### **Other outcome measures:**

Anonymous data will be drawn from the medical records. It will consist of the number of time elder abuse have been recorded in the designated place in the digital medical record for each participating clinic. The validity of this data has not been established and it will therefore be considered an experimental outcome but could potentially be an objective assessment of whether the intervention leads to increased identification of patients subjected to elder abuse.

Some items in REAGERA-P does not directly measure any of the learning objectives of the education but could potentially be affected by the intervention and will hence also be considered. They are as follows:

- Proportion of respondents reporting that victims of elder abuse were given an adequate follow up.
- Proportion of respondents reporting suspecting elder abuse but refraining from asking questions.
- Proportion of respondents reporting changed working practice at follow up because of the education.

**Covariates** potentially affecting both the intervention effectiveness and the outcome will be considered. These include background characteristics of participants both on an individual and group level.

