## Statistical analysis

The background characteristics of participants will be explored using descriptive statistics and comparisons will be made between clusters to detect significant differences. Missing data will be analysed and, if appropriate, multiple imputations will be considered. Attrition analysis will be conducted using e.g., chi square test and student's t-test to detect differences between those lost to follow up and those retained.

In a stepped wedge trial, results are compared across unexposed and exposed observation periods in the clusters, similar to the control and intervention arm in a parallel cluster trial (K Hemming, Haines, Chilton, Girling, & Lilford, 2015). The primary effect of this study will hence be calculated by comparing the main outcome (propensity to ask questions about abuse) in all clusters pre-intervention with all clusters post-intervention. Both mean difference in reported frequency of asking questions and changes in proportion of participants that report ever having asked questions about abuse will be reported. For the continuous outcome a linear mixed effect model will be used and for the binary outcome a generalised linear mixed effect model. The models will consider repeated measures and include cluster as random effect to determine if the anticipated effect of the model is dependent on the cluster, i.e., unit or clinic. During a stepped wedge trial more and more clusters will gradually transition from unexposed to exposed status, meaning that observation in the exposed status will on average be of a later date than the unexposed observation (K Hemming et al., 2015). This may introduce a bias in the study considering that there may be underlying temporal trends affecting the outcome, e.g., an increasing awareness of elder abuse in society over time. Therefore, both intervention status and time will be included as fixed effects in the models. Also, models will be adjusted for covariates, e.g., background characteristics, significantly associated with the outcome.

[figure not shown]
We propose that the education will work by participants overcoming personal and organizational barriers towards asking older patients questions about abuse. The items in REAGERA-P used to evaluate the effect on the different barriers and facilitators are described in figure 1 and they will be included in linear models (for continuous outcome) and generalised linear models (for binary

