outcomes) to determine the effect of the intervention on these outcomes. If results support the theoretical model, efforts will be made to test if changes in perceived barriers mediate a potential effect of the intervention on the primary outcome, i.e., asking questions about abuse.

[figure not shown]
Data from the medical records will be retrieved for the following periods a) 6 months pre-intervention, b) 0-6 months post intervention and c) 6-12 months post intervention. A linear mixed effect model will be used to investigate changes concerning how many victims are identified pre- and post-intervention at the participating clinics.

In all models, we will strive for parsimony; analysis will therefore be performed to determine which variables to include in multivariate analysis and only covariates that significantly affect the model will be included. Assumptions for models will be assessed graphically and, if needed, bootstrapping will be used to ensure model robustness. Significance level will be set at  $p=0.05$  and results will be reported with 95% confidence intervals.

**Figure 1.** Theoretical model. An illustration of the alignment between learning activities (yellow), learning objective, that is, barriers and facilitators on a personal (green) and organisational (blue) level as well as evaluation (red). EA, elder abuse; REAGERA-P, Responding to Elder Abuse in GERiatric care—Provider questionnaire.

**Figure 2** Design of the study and data collection points. An incomplete stepped wedge trial is planned. All clusters are measured pre-intervention (yellow squares=baseline and in conjunction with the educational day) and post-intervention (blue squares=at 6–8 months and 12–14 months of follow-up). Time of intervention is denoted by the red contour.

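### Does the medical-record model leave out calendar time, so that a background trend could pass for an effect of the education?

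*Combined protocol and SAP*

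**What the plan says.** Under Other outcome measures, the protocol plans to extract "the number of time elder abuse have been recorded in the designated place in the digital medical record for each participating clinic". It says that the validity of these data has not been established and labels the outcome experimental.

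Under Statistical analysis, the windows are "a) 6 months pre-intervention, b) 0-6 months post intervention and c) 6-12 months post intervention", and the model is given in one sentence: "A linear mixed effect model will be used to investigate changes concerning how many victims are identified pre- and post-intervention at the participating clinics". No fixed effects are listed there, not even intervention status.

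Earlier in the same section, after explaining that exposed observations fall later on average and that temporal trends may bias the study, the plan states that "both intervention status and time will be included as fixed effects in the models". The next sentence is "Also, models will be adjusted for covariates, e.g., background characteristics, significantly associated with the outcome". Under Other outcome measures, covariates are described with the words "These include background characteristics of participants both on an individual and group level".

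After the record model comes a parsimony rule for all models: "analysis will therefore be performed to determine which variables to include in multivariate analysis", and "only covariates that significantly affect the model will be included".

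**The concern.** Three features together look like a gap.

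- The windows are set relative to each clinic's own intervention date, so pre always precedes post. This is the ordering that the plan itself identifies as a source of bias.
- The commitment to a time effect stands in the paragraph on the main outcome, not beside the record model.
- The parsimony rule covers all models, speaks of variables as well as covariates, and does not expressly exempt time. With few clinics, a test for time has little power, so a rule that kept time only when significant would often drop a real trend.

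At stake would be a pre/post difference in recorded abuse that reflects rising awareness in society and not the education. Related questions are whether counts should be divided by patient volume, how the mixed-centre cluster 9 fits an outcome counted per clinic, and why Study design and the note to Figure 2 number the replacement primary care centre differently.

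**Working it through.** **Reading the text.** The documents give no figure for this outcome to reproduce, so the wording comes first.

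1. The reason given for including time is trial-wide (temporal trends biasing the study), and the record model is another mixed model in the same section. Its silence on fixed effects extends to intervention status, which it plainly must contain. The sentence is therefore shorthand, not a full specification.
2. The plan puts status and time in first and then adds covariates with the word Also. The deciding clause of the parsimony rule concerns covariates. If its mention of variables reached time, it would equally reach intervention status, which cannot be intended.

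**Size if time were nevertheless omitted.** Window midpoints relative to the intervention are −3, +3 and +9 months. Without time, both post windows have weight 0.5:

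- lag = (3 + 9)/2 − (−3) = 9 months = 0.75 year
- assumed rises of 5%, 10% and 20% per year give 0.75 × 5 = 3.75%, 0.75 × 10 = 7.5% and 0.75 × 20 = 15%.

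With linear or half-yearly calendar time in the model, the share of a linear trend absorbed is 0.

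**False positives.** These are simulations with no true effect. All inputs are assumed: 8 clinics, 24 counts, mean 5 to 40 per window, pure Poisson variation.

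| Yearly trend | Time kept only if significant | Time always in |
|---|---|---|
| 0% | 7–9% | 4–6% |
| 10% | 7–16% | 4–6% |
| 20% | 10–35% | 4–6% |

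With modest extra variation between windows (log-SD 0.3), the selection column becomes 6–7%, 7–8% and 9–11%.

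**Cost of including time.** This uses generalised least squares with a clinic random intercept, 8 clinics allocated 2/2/2/2 or 3/3/2 over half-year steps, and within-clinic correlation 0.5 to 0.9.

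- The standard error with time, relative to without, is 1.43–1.91 (linear) or 1.49–2.08 (half-yearly).
- Under the Poisson inputs, the standard errors for mean counts 5, 10, 20 and 40, as fractions of the mean, are 0.193, 0.139, 0.098 and 0.069 without time and 0.293, 0.229, 0.177 and 0.129 with it. Total error without time is √(SE² + bias²). At 20% per year and mean 20 this is √(0.098² + 0.15²) = 0.179 against 0.177 with time, essentially a tie. At mean 40 it is √(0.069² + 0.15²) = 0.165 against 0.129. In the other 10 of 12 combinations (5, 10 and 20% per year by four means), total error is larger with time.

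**What a single status term then estimates.** Without time, the effects at 0–6 and 6–12 months are weighted 0.5 and 0.5. With time, the weights range over 0.96 to 1.83 for the first window and +0.04 to −0.83 for the second. For the 2/2/2/2 layout, correlation 0.7 and linear time they are 1.274 and −0.274. True changes of 10% and 20% would then give 1.274 × 10 − 0.274 × 20 = 7.3%, below both.

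**Identifiability.** In an assumed layout of 9 clusters starting 3/2/2/2, adding intervention status to cluster and calendar period raises the design rank from 14 to 15, so the effect can be estimated. If time were coded as the pre, 0–6 and 6–12 month windows, the rank stays at 11 and it cannot.

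**The case for a change.** The best argument for acting is that a sentence costs nothing. The time commitment points grammatically to the main-outcome models, and extending it to the record model is an inference. The parsimony rule has no written exemption. An analyst who coded time as the three windows could not estimate the intervention effect. Step number would also be a poor substitute for dates, since the first-period primary care centres started later than the hospital clinics.

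The textual point stands: nowhere is time named for this model. It does not show an error, because the inference is the one the plan's own reasoning supports, and coding time as window would show itself at once as a rank-deficient fit. Nor is a forced time term a plain gain. It widens the interval, usually raises total error under the assumed inputs, and gives an unbiased estimate only when the effect is constant across both post windows.

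The related requests do not call for a change either. Rates would need visit or patient counts whose availability the documents do not show. With time in the model, false positives are about 5–6% whether counts or rates are used, so the benefit is precision only, unless volume shifts with the training. Records are collected per participating clinic, not per cluster, so how to treat cluster 9 is a choice for the analyst. The numbering mismatch is real: Study design has the replacement centre as new cluster 8, the note to Figure 2 as new cluster 6. It is a clerical slip to be tidied when the data are labelled, and it does not bear on the model.

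**Conclusion.** No change to the plan follows. The record-model sentence is brief, but the section around it already makes time a fixed effect for the reason that applies here, and it keeps covariates subject to selection apart from time. On that reading the bias from a common linear trend is zero. On the strained reading it is 0.75 of the yearly trend. How often that would yield a false positive rests wholly on assumed trends, counts, clinic numbers and variation, and the higher rates need a 20% yearly rise with no overdispersion.

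Two cautions remain for whoever fits and reports the model: time means calendar date, and a single status term alongside time assumes an equal effect at 0–6 and 6–12 months, although the test of no effect in either window remains valid. Both are ordinary matters of execution for an outcome that the protocol itself calls experimental, and the main and secondary outcomes do not depend on it.

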## Study design:

The design is a non-randomised stepped wedge trial, a type of controlled cluster cohort study in which the participants gradually move from control group to intervention group (Brown & Lilford, 2006; Copas et al., 2015). In this study, a cluster entail a whole clinic or a unit at a clinic and at the end of the study all clusters will have completed the intervention, i.e., participated in the education. Data will be collected for all participants both pre- and post-intervention. Figure 2 illustrates the study design, including time plan. The intervention was originally planned to be rolled out during four periods between September 2021 and June 2023 (figure 2) and an incomplete design was chosen, i.e., six periods are used, but every cluster is only included at four measurement points: at baseline, in conjunction with the education, at six months follow up and at twelve months follow up. Similar incomplete designs have been described previously (Copas et al., 2015; Karla Hemming, Lilford, & Girling, 2015). For practical reasons the primary care centres included in the first study period had to be included later than the hospital clinics, i.e., in December 2021. To avoid a data collection period during the summer vacation, their first follow up was conducted nine months post intervention. Thereafter they will fall into the same pattern of data collection at six months interval as the other clinics. The six months interval was chosen because it provides an intermediate (six months) and long-term (twelve months) follow up that allows for a reasonable evaluation of the effect of the education. The times of data collection is illustrated in figure 2.

One geriatric clinic (cluster 8) and one primary health care centres (cluster 9) who were included at baseline decided in 2023 not to participate in the study for logistic reasons, e.g., having to prioritize other training for the staff. Therefor another primary health care centre was included (new cluster 8) and one training day was also open to participants from various primary health care centres (new cluster 9). For these clusters there is therefore no baseline data available, only pre-intervention data. In addition, the data collection phase had to be prolonged until September 2023.

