### **Sample size**

Cluster sample size was calculated using the Shiny CRT Calculator web application (Karla Hemming, Kasza, Hooper, Forbes, & Taljaard, 2020). Significance level was set to 0.05 and power to 0.8. We planned for a three-step intervention and used the discrete time decay. Initially we had planned a complete four period stepped wedge design and hence, that was used in the sample size calculation together with the discrete time decay. Divergent cluster sizes were expected and coefficient of variation for a cluster size was set at 0.5. Results from a pilot study (Johanna Simmons, Motamed, Ludvigsson, & Swahnberg, 2022) was used to estimate cluster auto correlation at 0.6. Proportion

was set as outcome, and we used data from the pilot study to estimate the proportion under control at 0.26 and the proportion under intervention at 0.56. A cluster size of 10 then suffice to reach adequate power. Our smallest expected cluster has 31 participants and hence even with a response rate of less than 40% this is sufficient.

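### The experimental medical-record outcome is a raw count per clinic with no patient-volume denominator, so a volume change that coincides with training would be read as a change in identification

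*Combined protocol and SAP*

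**What the plan says.** All references are to the combined protocol and SAP.

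- **Outcome.** Under Other outcome measures, the record data are "the number of time elder abuse have been recorded in the designated place in the digital medical record for each participating clinic". Because validity is not established, "it will therefore be considered an experimental outcome", although the same paragraph hopes that it may give an objective view of identification.
- **Windows and model.** Under Statistical analysis, the data cover "a) 6 months pre-intervention, b) 0-6 months post intervention and c) 6-12 months post intervention". The model follows directly: "A linear mixed effect model will be used to investigate changes concerning how many victims are identified pre- and post-intervention at the participating clinics".
- **Covariates.** On these the plan says: "These include background characteristics of participants both on an individual and group level". The participants are staff. Patient volume is not named, and neither is a rate, an offset or a count distribution.
- **Time and cluster.** Fixed effects for intervention status and time, and a random effect for cluster, are described for the main-outcome models. They are not restated for the record model.
- **Model checks.** For all models the plan foresees graphical checks, with bootstrapping as a fallback.
- **Size.** Under Sample size, "Divergent cluster sizes were expected", with a coefficient of variation (CV) of 0.5. This describes study participants, not patients.

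**The concern.** The expected number of entries is the number of patients seen multiplied by the rate at which abuse is identified and recorded. The training is meant to change the rate. The planned data contain only the product, so the two factors cannot be separated afterwards. If a clinic sees more patients after training than before, its count rises even when staff record exactly as they did.

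The linear scale adds a second, smaller difficulty. If training multiplies the rate by a common factor, the added number of entries is proportional to clinic size, so large clinics contribute more to an average absolute change.

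At stake is the one outcome in the plan that does not rest on self-report. Without a denominator, a rise in entries cannot be told apart from a rise in workload.

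**Working it through.** **What can be reproduced.** The plan states no count, rate, volume or power for this outcome, so there is no figure of its own to reproduce. All volumes and rates below are assumptions. From the documents come the three six-month windows, the numbering of clusters up to 9, and the CV of 0.5 (for staff).

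**1. Volume change at a constant rate.** Count = volume × rate. With a rate of 2 per 1,000:

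| Patients before | Entries before | Entries after +20% volume | Difference | Rate ratio |
|---|---|---|---|---|
| 1,000 | 2.0 | 2.4 | +0.4 | 1.00 |
| 5,000 | 10.0 | 12.0 | +2.0 | 1.00 |
| 20,000 | 40.0 | 48.0 | +8.0 | 1.00 |

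The count always rises by 20%, and the absolute error grows with the clinic.

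**2. Effect on the test.** A simulation used nine clinics and three windows, with a mean of 3,000 patients per clinic and window, 2 entries per 1,000, volume CV 0.5, Poisson scatter and an unchanged rate. The linear model had clinic effects (fixed effects standing in for a random intercept). The comparator was a Poisson model with a log(volume) offset.

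| Volume change at training | Linear, no time term: estimate, rejection | Linear with time: estimate, rejection | Offset model: rejection |
|---|---|---|---|
| none | 0.0, 7% | 0.0, 4% | 5 to 7% |
| +20% | +1.3, 17% | +1.4, 9% | 6% |
| +50% | +3.1, 69% | +2.9, 15% | 6% |

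The time term leaves the false estimate about where it was. Rejection falls because the estimate is less precise. A step in volume that coincides with training cannot be separated from the intervention without a denominator.

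**3. Volume changes that do not follow training.** With time in the linear model, a trend shared by all clinics of +10% or +20% per half-year gave mean estimates of 0.03 and −0.16, with rejection of 4% and 3% (400 runs each). Clinic-specific random variation of about 20% gave a mean of 0.04 and rejection of 7%. These changes add noise and little bias.

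**4. Weight of the largest clinic.** Under a common rate ratio, a clinic's share of the mean change is its volume divided by total volume. An equal share among nine is 1/9 = 11%. The largest clinic's share averages about 21% at CV 0.5 (10th to 90th percentile 16 to 26%) and 31% at CV 1.0. If one clinic is ten times each of the others, it is 10/18 = 56%. With a true rate ratio of 2 at CV 0.5, dropping the largest clinic lowers the linear estimate from 6.4 to 5.7, or by (6.4 − 5.7)/6.4, about 10%.

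**The case against.** Several stronger readings are tempting, and the documents do not support them.

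- **That the largest clinic drives the result.** If entries per half-year ranged from 0.5 to 20 with a mean of 4.9, the largest of nine clinics would supply 20/(9 × 4.9) = 45%. That figure only restates the assumed range. The documents give neither entry counts nor patient volumes. At their one stated spread, which is for staff, the share is about 21%. The note to Figure 2, where one cluster fell from 60 planned participants to seven, describes voluntary registration and says nothing about patient volume.
- **That season biases the comparison.** The phrase "To avoid a data collection period during the summer vacation" concerns a survey round, not patient activity. The windows before training and at 6 to 12 months cover the same calendar months one year apart, so season largely cancels between them. Only the middle window differs. With a 20% seasonal swing, pooled post minus pre is (1.2 + 1.0)/2 − 1.0 = +0.1 of the seasonal low for a clinic trained at one time of year, and (1.0 + 1.2)/2 − 1.2 = −0.1 for one trained half a year later. Staggered training offsets this at least in part.
- **That every volume change becomes an effect.** A shared trend is largely absorbed if time is in the model. The bias needs a sustained change that coincides with training, and the documents give no evidence that one occurred.
- **That the linear model is invalid.** In a separate simulation of 4,000 runs with stable volumes, it held type I error at 4.0 to 4.9%. A log-rate model scaled for overdispersion ran at 2.2 to 5.0%, but reached 9.1% with strong size spread plus overdispersion. Power, linear against log-rate, was 46% against 55% (rate ratio 1.5), 83% against 89% (rate ratio 2), and 17.5% against 16.3% in a very sparse case. The simulation with a time term in the working above showed a larger gap at a rate ratio of 2 (37% against 67%), but under pure Poisson scatter. The gain depends on the setting, so the link function is secondary.

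The planned checks and bootstrapping do address unequal scatter. They cannot supply a denominator that was not extracted, and that part of the concern stands. The experimental label also stands and limits how much the point matters.

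**Conclusion.** The concern holds in a limited form. The outcome is a raw count, the model is linear, and no volume is collected, so a change in a clinic's volume that coincides with training would be counted as a change in identification. The error is proportional: a 20% volume rise at an unchanged rate reads as 20% more entries. Large clinics can weigh disproportionately on this scale, roughly twice an equal share if patient volumes vary as staff numbers were expected to. Both sizes rest on assumed volumes. Protection against a shared trend depends on a time term that the plan does not clearly extend to this model.

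The severity is minor. The outcome is experimental, it is neither the main nor a secondary outcome, and the sample size does not rest on it.

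**What to change.** - **Other outcome measures:** with each count, extract the number of visits (or unique older patients) at the same clinic in the same window, as an anonymous aggregate. State whether the unit counted is an entry or a person. This section counts recordings, while Statistical analysis speaks of victims, and one person may be recorded more than once.
- **Statistical analysis:** analyse the rate with a log-link count model (Poisson with estimated overdispersion, or negative binomial), with log(visits) as offset, a clinic effect, and intervention status and calendar time as fixed effects. Use a small-sample t reference. Report a rate ratio with its 95% confidence interval and a leave-one-clinic-out check.
- **New cluster 9:** it was open to staff from various primary care centres, so neither its count nor its denominator is defined. State which centres make it up for this outcome, or leave it out.

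The cost is one further aggregate figure per clinic and window, assumed to be available from the record system, plus a few sentences in the plan. The drawback is an imprecise overdispersion estimate with about nine clinics.

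### Covariates, including clinic setting, are kept only if significant in a non-randomised design; the set for the participant-level models should be fixed in advance

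*Combined protocol and SAP*

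**What the plan says.** Under Study design: "The design is a non-randomised stepped wedge trial". The Covariates paragraph at the end of Other outcome measures says that covariates "potentially affecting both the intervention effectiveness and the outcome will be considered", and adds: "These include background characteristics of participants both on an individual and group level". It lists no items and does not mention clinic setting.

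Statistical analysis then sets the rule for inclusion twice. For the main-outcome models, "models will be adjusted for covariates, e.g., background characteristics, significantly associated with the outcome". For all models, in the interest of parsimony, "only covariates that significantly affect the model will be included". No test is named. Background characteristics are described first, and then "comparisons will be made between clusters to detect significant differences". Some terms are exempt from selection: cluster is a random effect, and "both intervention status and time will be included as fixed effects in the models".

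Study design also reports that "the primary care centres included in the first study period had to be included later than the hospital clinics", and that those centres had their first follow-up at nine months. Two clusters were replaced by primary care clusters that have no baseline data. The section numbers these 8 and 9; the note to Figure 2 numbers them 6 and 9.

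The main outcome is to be analysed and reported both as ever/never and as a count. Neither version is named as deciding. The sample size rests on the proportion.

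**The concern.** Without randomisation, balance between early and late clusters cannot be assumed. A variable that the design links to timing and to missing measurements is a candidate for adjustment on design grounds. Whether its coefficient reaches p<0.05 is a different question, and with about nine clusters the answer depends mainly on how many clusters there are and on which test is used. The rule also means that the covariate set can be settled only after the outcome data have been seen.

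The point is mainly about group-level covariates. With around 700 participants, strong individual-level covariates would usually pass the screen.

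A small related gap is that, if the two versions of the main outcome disagree, the plan does not say which one answers aim 1.

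**Working it through.** The plan gives no figure for covariate selection, so there is none to reproduce. The yardstick is its planned effect: 0.56 − 0.26 = 0.30 (Sample size).

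**Inputs from the documents.** Six periods with four measurement points per cluster; first-period primary care followed up first at nine months; two primary care replacements without baseline; seven registrants in cluster 8; around 700 participants.

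**Assumed, because Figure 2 is not shown.** Nine clusters, three per step, and three steps (as in Sample size, although Study design mentions four roll-out periods). Education falls in period 2, 3 or 4. The ICC is 0.02 to 0.10. The true setting difference is 10 points (0.26 v 0.36, mean 0.31).

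**Step 1: chance that setting is kept.** For five clusters against four, with n observations per cluster,

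SE = √{0.31 × 0.69 × [ICC + (1 − ICC)/n] × (1/5 + 1/4)}.

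- ICC 0.02, n = 180: SE = √{0.2139 × (0.02 + 0.98/180) × 0.45} = 0.0495, so 0.10/SE = 2.02. Chance of significance: 0.52 (Wald z), 0.41 (t, 7 df).
- ICC 0.10, n = 80: SE = 0.1035, so 0.10/SE = 0.97. Chance: 0.16 (Wald z), 0.13 (t).
- Participant-level screen ignoring clustering, 700 × 5/9 = 389 v 311: SE = √(0.26 × 0.74/389 + 0.36 × 0.64/311) = 0.0351, ratio 2.85. Chance: 0.81.

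The choice of test, which the plan leaves open, moves the answer from 0.13 to 0.81.

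**Step 2: bias if setting is dropped.** In a linear approximation, the share of the setting difference that leaks into the intervention effect is the intervention element of (ΣX′V⁻¹X)⁻¹ΣX′V⁻¹s. Here X holds six period indicators and intervention status, and s = 1 for primary care. V = [ICC + (1 − ICC)π/m]J + [(1 − ICC)(1 − π)/m]I, where J is the all-ones matrix and I the identity, with m = 20 or 45 respondents per cluster-period and participant variance share π = 0, 0.3 or 0.5.

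Both sections describe cluster 8 as primary care, so it is held there. Step 1 has two primary care clusters to one hospital, or one to two. The replacements are 8 and 9, or 6 and 9. Cluster 8 has seven respondents or full size. The remaining clusters take either setting. That gives 2 × (16 + 8) × 2 = 96 layouts. Removing 4 with fewer than two hospital/geriatric clusters leaves 92, or 92 × 2 × 3 × 3 = 1,656 combinations per grid.

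| Period grid | Leakage | Median size | Lowest 95% CI coverage |
|---|---|---|---|
| Common six-month grid | −32% to +6% | 5% | 92% |
| Nine-month follow-up placed on the grid | −37% to −1% | 8% | 91% |
| December 2021 education counted in period 3 | −41% to −1% | 10% | 90% |

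Coverage is Φ(1.96 − b/SE) − Φ(−1.96 − b/SE), where b is the bias for a 10-point difference. A negative share means that the effect is understated if primary care asks more often than hospital clinics, and overstated if it asks less often.

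**Step 3: in points.** On the first two grids, 10 × 0.05 = 0.5 and 10 × 0.08 = 0.8 points are typical. The worst case over all three is 10 × 0.41 = 4.1 points, against 30.

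**Step 4: cost of always fitting setting.** On the first two grids the standard error rises by under 1% (median) and by at most 7% and 9%. On the December reading the same calculation gives just over 1% and at most 11%.

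**Step 5: separate simulation.** Assumed six-period layout, nine clusters, 20 respondents per cluster-period, cluster autocorrelation 0.6, true intervention effect zero, 3,000 runs per scenario.

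- *Settings spread evenly over steps:* omitting setting gives a bias of at most 0.008 for setting differences of 0.10 to 0.20, and type I error stays near 5%.
- *Hospitals mostly early, 10-point difference, no setting-specific trend:* the bias at ICC 0.02 is 0.055 with setting omitted, 0.022 under the significance rule and 0.001 with setting always fitted. At ICC 0.10 the sizes are 0.036, 0.019 and 0.001.
- *Hospitals mostly early, with a setting-specific trend:* always fitting setting still leaves a bias of up to 0.024.

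**The case against.** The strongest reply is that no harm is shown for this trial. The plan does not name setting as a covariate and reports no setting difference in the outcome. It places both settings in the first period. Time and cluster are always in the model and absorb most of any imbalance. The leakage figures assume that setting is always dropped, whereas the rule sometimes keeps it. They also come from a linear model, while the ever/never outcome will use a generalised linear mixed model. The Covariates paragraph does start from a subject-matter criterion.

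Most of this stands, and it limits the size of the point. It does not rescue the rule: the criterion names no items, every candidate still has to pass a significance test, and a random cluster effect does not fully remove between-cluster differences.

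Two stronger readings are tempting. A reader might infer that the rule inflates false positives materially, since the simulation gave a type I error of about 7% to 12% (about 4% to 6% with setting always fitted). That arises when hospitals go mostly early, which no section states. A reader might also infer that two versions of the main outcome, each tested at 0.05, raise the error to 7% to 9% (9.75% if independent: 1 − 0.95²). That holds only if either result alone could count as success, which the plan does not say. Both versions will be reported.

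**Conclusion.** The concern holds, at low to moderate severity. In a non-randomised design, the plan leaves adjustment for a design-linked characteristic to an unspecified test that may have little power. The likely bias is small: typically 0.5 to 0.8 points and at most about 4 points per 10-point setting difference if setting is dropped, and less under the rule as written because setting is sometimes kept. It would not overturn a 30-point effect, though it would weigh more against a smaller one.

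The sizes rest on the assumed layouts, ICC range and 10-point difference, and on reading setting as a group-level characteristic. The wording of the rule rests on none of these. The outcome-version point is a minor addition and does not raise the severity.

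**What to change.** **Participant-level REAGERA-P outcome models.** In both places in Statistical analysis, replace the significance rule with a set fixed before outcome data are examined and kept whatever the p-values: intervention status, time, setting (hospital/geriatric versus primary care), profession, and individual background items listed by name from REAGERA-P. Report alongside it the model with intervention status, time and cluster only.

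**Medical-record model.** This uses anonymous counts per clinic, so individual items cannot enter. Fix only clinic-level terms: time and, if feasible, setting.

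**Main outcome.** Name the dichotomous version as the primary analysis and the count as supportive.

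**Cost.** SAP wording, one cluster-level degree of freedom for setting with the standard-error increase given above, and a few degrees of freedom for the individual items. The count alone could no longer support a claim of success.

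**Limit.** A setting main effect does not remove a setting-specific time trend or the difference between a nine-month and a six-month first follow-up. The SAP should say so.
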